5.0 Study Procedures

Study Design

Each subject will be studied using a double-blind, placebo-controlled, crossover design. Figure 3 illustrates the flow through the study for an individual participant.

Study Procedures

Participants will be asked to fast for 12 hours prior to each study day.

On Study Day 1 (Pre-test), all study participants will complete a screening / phenotyping examination. The participant will undergo a complete history, physical exam, resting EKG and phlebotomy for screening and phenotyping laboratories (complete blood count, liver and kidney function tests, electrolytes, fasting glucose and insulin). They will also practice the entire isokinetic dynamometer exercise test.

To minimize variation in baseline $\text{NO}_3^-/\text{NO}_2^-/\text{NO}$ levels, participants will be instructed to consume their normal diet (aside from the BRJ supplement) throughout the study. Participants will, however, be asked to avoid consumption of high NO_3^- foods (e.g., beets, spinach, collard greens) the evening prior to testing. This approach is justified based on the short half-life of NO_3^- in plasma (i.e., ~8 h) as well as previous research demonstrating that even a chronic increase in dietary NO_3^- intake up to 2.5 mmol/d (i.e., ~3x normal dietary NO_3^- intake in the US) has no significant influence.⁵⁶ Participants will be asked to refrain from chewing gum, alcohol, and caffeine-containing food/drinks for 24 h prior to each remaining visit. Participants will also be instructed to refrain from use of an antibacterial mouthwash throughout the study, since this would limit conversion of NO_3^- to NO_2^- by bacteria in the oral cavity.⁵⁷ Participants will be asked to fast for 12 h prior to each remaining study visit.

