On Study Day 2, participants will undergo phlebotomy for plasma NO_3^- and NO_2^- measurement, and have their breath NO level determined. (Breath NO will be measured as a biomarker of increases in whole-body NO production in response to dietary NO_3^- intake.^{52,53}) The subject will then ingest 3.3 mL/kg of a commercial concentrated beetroot juice (BRJ) supplement (Beet It Sport®, James White Drinks, Ipswich, UK) either: 1) essentially devoid of NO_3^- (placebo); 2) containing (as determined by previous direct measurement) 91 $\mu\text{mol}/\text{mL}$ NO_3^- (thus total dose = 300 $\mu\text{mol}/\text{kg}$, or 21 mmol in a 70 kg subject); or 3) an equal mixture of the placebo and NO_3^- -containing BRJ products. The placebo, which is prepared by the company by extracting NO_3^- from BRJ using an ion exchange resin, is indistinguishable in packaging, color, taste, texture, and smell from the standard product, and does not alter plasma $\text{NO}_3^-/\text{NO}_2^-$ or breath NO concentrations or the physiological responses to exercise.²⁹⁻³¹ Additional blood and breath samples will be obtained 1 and 2 h later, as well as blood pressure and heart rate, after which time the subject will have the Vmax and Pmax of the knee extensor muscles of their dominant leg determined via isokinetic dynamometry (see below). The timing of all measurements has been chosen to correspond to peak plasma $\text{NO}_3^-/\text{NO}_2^-$ concentrations and breath NO levels, which reach a maximum 2-3 h after ingestion.²⁹⁻³¹

On Study Days 3 and 4, participants will be asked to return to undergo the same studies as described above for Study Day 2.

Study Methods

Measurement of NO₃⁻ in each batch of BRJ w/ or w/o NO₃⁻: The NO₃⁻ content of each batch of BRJ w/ or w/o NO₃⁻ will be determined using high performance liquid chromatography (HPLC) (ENO-30, Eicom USA, San Diego, CA).

Measurement of plasma NO₃⁻, NO₂⁻, and breath NO: Venous blood samples will be obtained prior to consumption of BRJ w/ or w/o NO₃⁻ and every hour thereafter for 3 hours, plasma rapidly separated by centrifugation, and frozen at -80° C until subsequently analyzed for NO₃⁻ and NO₂⁻ concentration using HPLC as described above. Breath NO levels will be measured at the same time points using a portable electrochemical analyzer (NIOX VERO, Circassia Pharmaceuticals, Chicago, IL).

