7.0 Statistical Considerations

Statistical analyses: Normality of data distribution will first be tested using the D'Agostino-Pearson omnibus test. Analysis of individual endpoints will then be conducted using a mixed model analysis of variance (ANOVA) approach, with dose, trial number, and sequence as fixed effects and subject as a random effect to account for repeated measurements. As a preliminary analysis, carryover will be evaluated by testing the effect of sequence, i.e. does the effect of dose depend on trial. Assuming a sufficient washout period, i.e., no carryover effect, analysis of dose will proceed using all trials. Dose effects will be determined from ANOVA model results. A P value of <0.05 will be considered significant.

Calculation of sample size/power analyses: Our proposed sample size (i.e., n=20) for this pilot, proof-of-concept study has been chosen primarily based on budgetary considerations and the 1 y duration of the project. G*Power[©] version 3.1.9.4⁵⁹ was used to determine the sample size required to provide a power (i.e., 1- β) of 0.90 assuming an effect size (i.e., Cohen's d) of 1.5. This effect size is based on the n=7 healthy older subjects that we have studied to date and is roughly the same as that we have previously observed for the effects of dietary NO₃⁻ on muscle contractile function in younger subjects.^{29,30} These calculations demonstrated that with $\alpha=0.05$, n=15 would be sufficient to provide the chosen power. The power that a sample size of n=15 would provide to detect other effect sizes is shown in Figure 4. Based on these calculations, we will enroll 20 subjects to allow for subject drop-out.

Potential limitations and alternatives considered: A possible limitation of the proposed study is the lack of direct demonstration that dietary NO_3^- results in an increase in NO specifically within muscle. This is because 1) the biological half-life of NO is extremely short (i.e., seconds), precluding measurement of its concentration in human tissue samples, and 2) existing stable isotopic methods only measure the rate of NO production via the NOS pathway, and not the enterosalivary pathway. We will, however, measure changes in plasma $\text{NO}_3^-/\text{NO}_2^-$ and breath NO (a biomarker of whole-body NO bioavailability) levels in response to dietary NO_3^- . We therefore do not consider the absence of direct measurements of plasma or muscle NO a significant limitation.

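### The carryover check in Section 7.0 joins two different tests, says almost nothing about washout, and has no stated response to a significant result (minor)

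*Combined protocol and SAP*

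**What the plan says.** Section 7.0 fits a mixed-model ANOVA to each endpoint "with dose, trial number, and sequence as fixed effects and subject as a random effect to account for repeated measurements". As a preliminary step, "carryover will be evaluated by testing the effect of sequence, i.e. does the effect of dose depend on trial". The text then continues: "Assuming a sufficient washout period, i.e., no carryover effect, analysis of dose will proceed using all trials". Dose effects are taken from the ANOVA model, and "A P value of <0.05 will be considered significant". No sentence says what follows if the carryover check is significant.

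Section 5.0 describes three treatment visits (Study Days 2 to 4) and gives a plasma nitrate half-life of about 8 h. On the first of these days, before the juice is taken, "participants will undergo phlebotomy for plasma NO_3^- and NO_2^- measurement, and have their breath NO level determined"; Study Days 3 and 4 repeat the same procedures. On layout, "Figure 3 illustrates the flow through the study for an individual participant". That figure is not shown in the available text, so the visit interval and the set of treatment sequences may be given there.

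**The concern.** The sentence defining the check joins two tests with an i.e. A sequence main effect compares groups of subjects who received the doses in different orders, and is judged against between-subject error. Whether the dose effect depends on trial is a dose-by-trial interaction. The two are related: sequence means carry half of the interaction's sum of squares with either 3 or 6 sequences. They are not the same test, however. The listed model contains neither the interaction nor a term for the previous dose. Two analysts could run different checks and both claim to follow the plan.

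Two things are at stake. First, a non-significant result could be cited as showing adequate washout when it shows almost nothing. Second, with no carryover at all, the check will still be significant about 5% of the time for each endpoint, and the response would then be chosen after seeing the data.

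**Working it through.** The plan gives no power figure for this check, so there is none to reproduce.

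**Inputs from the documents.** Three doses in three trials; alpha 0.05; n = 15 (stated requirement) to 20 (enrolled); half-life about 8 h; effect size d = 1.5 (Section 7.0), read here as a paired standardised effect dz. Pilot Vmax change 9 ± 5%, n = 6: t = 9/5 = 1.8 on 5 df gives P = 0.13 as printed, so the ± is a standard error and dz = 1.8/√6 = 0.735. Pilot Pmax change 2 ± 3%: dz = (2/3)/√6 = 0.27.

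**Assumptions (not in the available text).** 3 cyclic or 6 sequences; between/within SD ratio r = 1 to 5; carryover equal to a fraction λ of the previous dose's effect; middle dose giving half the high-dose effect (linear) or all of it (plateau). Section 1.0 describes a plateau for aerobic exercise in young men and says it is unknown whether one exists for muscle contractile function.

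**Power of the sequence test.** Every subject receives all three doses, so direct effects cancel between sequences. Carryover adds λ times the effects of the first two doses, so sequence means differ only by −λ × (effect of last dose)/3. Writing Δ for the high-dose effect, Δ² = 2·dz²·σw². The noncentrality is

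n × (λ²/9) × v × 2·dz² / (r² + 1/3),

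where v is the variance of the three dose effects in units of Δ: 1/6 for (0, ½, 1) and 2/9 for (0, 1, 1).

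Most favourable case: n = 20, 3 sequences, dz = 1.5, r = 1, λ = 0.5.
- Linear: 20 × 0.25/9 × 1/6 × 4.5/1.333 = 0.3125; power on F(2, 17) is 7.0%.
- Plateau: 20 × 0.25/9 × 2/9 × 4.5/1.333 = 0.417; power is 7.7%.

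Uneven allocation of 20 subjects to 3 sequences moves these by about 0.1 percentage point. Over the whole assumed range:

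| Carryover λ | Power, sequence test |
|---|---|
| 12.5% | 5.0-5.2% |
| 50% | 5-8% |
| 100% | 5-17% |

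With a linear response, the pilot Vmax effect gives at most 5.5% at 50% carryover, and the pilot Pmax effect at most 5.3% even at 100%. In the most favourable case, 80% power would need about 7,400 (plateau) to 9,900 (linear) subjects at 12.5% carryover, and about 470 to 620 at 50%.

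**Power of the dose-by-trial reading.** Tested within subjects at dz = 1.5, power is about 5-6% at 12.5% carryover, 6-18% at 50% and 9-59% at 100%. It becomes useful only for carryover far above what the half-life suggests.

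**Size of the bias.** With 6 balanced sequences, placebo is followed over in two thirds of its uses by each other dose as predecessor equally often, which adds λ(m + 1)/3 to its mean, where m is the middle-dose effect as a fraction of Δ. High dose gains λm/3. The difference is −λ/3. An 8 h half-life leaves 0.5³ = 12.5% at 24 h and 0.5⁶ = 1.6% at 48 h. If the effect tracks plasma nitrate, the bias is 12.5/3 ≈ 4% and 1.6/3 ≈ 0.5% of the effect, toward zero. With 3 cyclic sequences and a linear response it is also λ/3. With a plateau it is 0 or 2λ/3 depending on the direction of the cycle, so at most 8.3% and 1.0%.

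**What pre-dose nitrate can show.** Table 1 standard errors of 4 and 7 µmol/L at n = 7 give SDs of 4√7 = 10.6 and 7√7 = 18.5. Take a within-subject correlation of 0 or 0.5 and adjust for subject and trial. The 95% CI half-width for previous high dose versus previous placebo is then about 6.6-18.6 µmol/L. Against the Table 1 rise of 295 − 31 = 264 this is 2.5-7.1%, equivalent to a bias of 0.8-2.4% after dividing by 3. Power is 88-100% for the 24 h residue (264 × 0.125 = 33 µmol/L) and 6-18% for the 48 h residue (about 4 µmol/L), where the bias is about 0.5%. The dose behind Table 1 is not given, so these figures are approximate.

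**The case against.** The strongest reply is that low power for a very small effect comes with about 20 subjects, whichever test is used. That is correct: a previous-dose term also has only 5-7% power at 12.5% carryover. With 3 cyclic sequences that term has the same power as the within-subject dose-by-trial test. Low power alone is therefore not the complaint. The complaint is that the check is described as two tests, is not in the model, and is offered as the evaluation of washout when better evidence is already being collected.

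A reader might infer that the dose analysis is undefined. That follows only if the sentence on washout is a condition for proceeding. It can equally be read as a stated assumption. On that reading the dose analysis is fully specified, and only the response to a positive check is missing.

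A reader might also infer that carryover threatens the trial's result. The documents do not support this: visits are on separate study days and the half-life is about 8 h. Nor can it be said that the plan omits the visit interval or the sequences, since Figure 3 may give both. If it shows an interval of several days, nitrate carryover is immaterial and only the open response to a chance significant result remains.

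**Conclusion.** The point holds, at minor importance. The check is mis-specified whatever Figure 3 shows, because the ambiguity and the missing model term lie in Section 7.0 itself. That its power is close to alpha rests on the assumed sequence sets, SD ratios and effect sizes, but it holds across all of them for carryover up to 50%. The consequence is an uninformative check and an open analytic choice in roughly 5% of null tests per endpoint, not a large bias. The estimate of about 4% at 24 h and 0.5% at 48 h depends on the muscle effect following plasma nitrate, and on 6 sequences or a roughly linear dose response.

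**What to change.** In Section 7.0:

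1. Delete the sequence test as a preliminary check. State that dose is analysed on all three trials with the mixed model, whatever any carryover check shows.
2. Assess washout by comparing pre-dose plasma nitrate, nitrite and breath NO on Study Days 2 to 4 by the previous visit's dose, adjusted for subject and trial. Report differences with 95% CIs.
3. If 6 sequences are used, a previous-dose term may be added as a sensitivity analysis, reported beside the unadjusted estimate, which stays primary. With 3 cyclic sequences, omit it.
4. Make neither check a condition for the dose analysis. Give the visit interval and sequence set in the text if Figure 3 does not.

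Cost: a few sentences and a small extra analysis, with no new data. The previous-dose term raises the standard error of high dose versus placebo by about 11-14% with 6 sequences. With 3 cyclic sequences it more than doubles it (from 0.317 to 0.716 within-subject SDs at n = 20) and adds no power over the dose-by-trial test. The biomarker comparison shows washout of exposure; it cannot exclude a functional effect that outlasts plasma nitrate.

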Using methods essentially identical to those to be employed in the proposed experiments (see below), we previously demonstrated that acute dietary NO_3^- intake increased maximal knee extensor speed (Vmax) and power (Pmax) in 12 healthy, younger men and women by $11\pm 5\%$ ($P<0.05$) and $6\pm 3\%$ ($P<0.05$), respectively.²⁹ We observed similar dietary NO_3^- -induced improvements in muscle speed and power in 13 athletes performing multi-joint, multi-muscle, i.e., sprint cycling, exercise.³⁰ Lastly, we found even greater increases in Vmax and Pmax (of $12\pm 5\%$, $P=0.09$, and $13\pm 4\%$, $P<0.05$, y) in nine middle-aged patients with systolic heart failure (HF).³¹

[figure not shown]
Using the same methods, we have also recently determined the effects of dietary NO_3^- in six healthy men and women 64-79 y of age. As shown in Table 1, plasma NO_3^- and NO_2^- and breath NO increased ($P<0.05$) by $1309\pm 188\%$, $268\pm 91\%$, and $142\pm 19\%$, respectively, by 2 h after ingestion, and all three remained elevated for the remainder of the experiment. These findings are consistent with our previous research.²⁹⁻³¹ This increase in NO bioavailability resulted in a $9\pm 5\%$ increase in maximal muscle speed, i.e., Vmax (Fig. 2, *left panel*), with five out of the six subjects demonstrating an improvement. This increase, however, was not statistically significant (i.e., $P=0.13$), and maximal muscle power, i.e., Pmax, improved on average by only $2\pm 3\%$.

Table 1. Changes in plasma NO_3^- and NO_2^- and breath NO in response to dietary NO_3^- intake in older study participant.

	Trial	Pre	1 h	2 h	10 min post exercise
Plasma NO_3^- ($\mu\text{mol/L}$)	Placebo	26 \pm 4	24 \pm 3	24 \pm 3	22 \pm 4
	Nitrate	31 \pm 7	285 \pm 27*	295 \pm 27*	282 \pm 33*
Plasma NO_2^- ($\mu\text{mol/L}$)	Placebo	0.21 \pm 0.03	0.26 \pm 0.06	0.26 \pm 0.06	0.20 \pm 0.03
	Nitrate	0.27 \pm 0.04	0.43 \pm 0.13	0.49 \pm 0.06*	0.56 \pm 0.10*
Breath NO (ppb)	Placebo	23 \pm 5	26 \pm 4	27 \pm 4	23 \pm 5
	Nitrate	27 \pm 4	49 \pm 7*	38 \pm 4*	52 \pm 10*

Values are mean \pm S.E. for n=7. *Nitrate trial significantly higher than Placebo trial at same time point (P<0.05).

(P=0.47) (Fig. 2, *center panel*). This is only 1/3rd as much as we previously found in younger Figure 2. Responses of Vmax (left panel) and Pmax (center and right panels) to dietary NO_3^- in older subjects.

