men and women.^{29,30} Closer examination of the data suggested that this diminished effect was due to an inadequate dose of NO_3^- , as there was a significant positive relationship between NO_3^- intake relative to body mass and the relative improvement in Pmax (Fig. 2, *right panel*). These preliminary results therefore suggest that older individuals remain responsive to NO_3^- , but that a higher dose may be required to elicit improvements in muscle contractile function.

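### The standardised effect of 1.5 attributed to the older pilot subjects is not supported by the pilot Vmax and Pmax results that the protocol prints

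*Combined protocol and SAP*

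**What the plan says.** Section 7.0 says the sample size of 20 was "chosen primarily based on budgetary considerations and the 1 y duration of the project". It then reports that G\*Power "was used to determine the sample size required" for power 0.90 at Cohen's d = 1.5 and α = 0.05, and concludes that "n=15 would be sufficient to provide the chosen power". Twenty will be enrolled to allow for drop-out.

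On the source of 1.5, it states: "This effect size is based on the n=7 healthy older subjects that we have studied to date". It adds that the value "is roughly the same as that we have previously observed for the effects of dietary" nitrate on muscle contractile function in younger subjects. It does not give the endpoint, contrast, test, sidedness or version of d (standardised by the SD of paired differences or by the SD within a condition).

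Section 1.0, Preliminary data, gives the older-adult muscle results for six subjects. Vmax rose 9±5%, "with five out of the six subjects demonstrating an improvement". Of this result the text says: "This increase, however, was not statistically significant" (P=0.13). Pmax rose 2±3% (P=0.47). Table 1, which holds plasma and breath markers only, is labelled mean ± S.E. for n=7. The section attributes the weak Pmax response to dose and suggests that "a higher dose may be required to elicit improvements in muscle contractile function".

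**The concern.** The comparison with younger subjects presents d = 1.5 as an effect on muscle function. An effect of that size, taken as a paired effect, would have been clearly significant even in six people, yet the same protocol reports non-significant Vmax and Pmax changes.

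A reader of Section 7.0 would conclude that 15 completers give 90% power for an effect already seen in older adults. If the printed pilot results are the better guide, that does not hold, least of all for Pmax, and a null Pmax result would be weak evidence of no effect. Section 7.0 also describes the trial as a first step towards designing larger studies, so the basis for its planning value should be traceable.

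**Working it through.** **Inputs.** Section 7.0: d = 1.5, power 0.90, α = 0.05, n = 15 (20 enrolled). Section 1.0: six older subjects, Vmax 9±5% (P=0.13), Pmax 2±3% (P=0.47). Two-sided tests are assumed, because sidedness is not stated.

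**1. The plan's own figure.** Power of a paired t-test comes from the noncentral t with n−1 df and noncentrality d√n. At d = 1.5:
- n=6: power 0.833
- n=7: power 0.908
- n=15: power 0.9997

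A paired test therefore needs 7, not 15. A two-sample test needs 11 per group. Fifteen appears only with settings the plan does not state, such as a two-sample test at α = 0.01 (15 per group, power 0.9005). Conversely, n=15 gives 90% power at a paired effect of 0.90.

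**2. What ± means in the older pilot.** Read as S.E., t = 9/5 = 1.80 on 5 df and P = 0.132, matching the printed 0.13. Read as SD, t = (9/5)√6 = 4.41 and P = 0.007, which does not match. Table 1 also labels ± as S.E.

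**3. Paired effects implied by the print** (paired d = t/√n).
- Vmax: 1.80/√6 = 0.735, or 0.739 from P=0.13. The 95% CI, from inverting the noncentral t on 5 df, is −0.21 to 1.62.
- Pmax: (2/3)/√6 = 0.272, or 0.319 from P=0.47.
- For comparison, a paired d of 1.5 would give t = 1.5√6 = 3.67 and P = 0.014 with six subjects, or t = 1.5√7 = 3.97 and P = 0.007 with seven.

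**4. Could a seventh subject explain it?** Let m and s be the mean and SD of the six, and x the unknown seventh value. Then mean₇ = (6m + x)/7 and SD₇² = [5s² + (6/7)(x − m)²]/6. Maximising mean₇/SD₇ over x:
- Vmax: m=9, s=5√6, best x≈22.9, so 10.98/12.35 = 0.89. With the most favourable rounding (9.5 and 4.5) it is 1.02.
- Pmax: 0.48 using the S.E., or 0.51 using P. With the most favourable rounding (2.5 and 2.5) it is 0.59.

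**5. Could another version of d explain it?** With equal SDs in the two conditions and within-person correlation ρ, between-condition d = paired d × √(2(1−ρ)). For ρ ≥ 0 this is at most 1.414 times the paired effect:
- Vmax: 0.735 × 1.414 = 1.04, or 1.017 × 1.414 = 1.44 with the best seventh subject and rounding.
- Pmax: at most 0.586 × 1.414 = 0.83.

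Neither reaches 1.5.

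**6. Power, two-sided paired test, α = 0.05.**

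| Basis | Paired d | n=15 | n=20 |
|---|---|---|---|
| Vmax as printed | 0.735 | 0.75 | 0.88 |
| Vmax, best seventh subject and rounding | 1.017 | 0.955 | 0.991 |
| Pmax as printed | 0.272–0.319 | 0.17–0.21 | 0.21–0.27 |
| Pmax, best seventh subject and rounding | 0.586 | 0.56 | 0.70 |

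**7. Detectable effect at 90% power.** For a simple paired test, d = 0.90 with 15 completers and 0.76 with 20. If the mixed model's pooled error is assumed to have 2n−4 df, the values are about 0.87 and 0.74.

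**The case against.** The strongest reply is that d = 1.5 may have a basis that is not printed. Section 7.0 names no endpoint, Section 5.0 also lists fatigue and recovery tests, and Figures 2 and 4 are not visible in the text reviewed. The only n=7 data printed are the markers in Table 1, and breath NO at 1 h gives a between-condition value of (49−26)/√(7×(7²+4²)/2) = 1.52. This stands as a limit: a reader might infer that 1.5 is proven wrong, and the documents do not show that. A marker effect, however, would not support power for muscle function, which is the Specific Aim.

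Second, six subjects say little about the true effect. The Vmax interval includes 1.5, and a higher dose than the pilot's may do better. Both points stand. But Section 7.0 presents 1.5 as based on subjects already studied, not as a projection to the trial doses.

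Third, a reader might infer that the comparison with younger subjects is also false. The documents cannot settle this. In heart failure (n=9), Vmax 12±5% is printed with P=0.09, whereas 12/5 on 8 df gives 0.043 and the least favourable rounding (11.5/5.5) gives 0.070. The printed ± and P therefore need not come from the same test, and no upper bound can be set for the younger subjects. The figures from the athlete study, the second comparator cited, are not printed on this scale. The same caution applies to the older pilot, although there the Vmax figures do agree with each other.

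Fourth, a reader might take the n=15 mismatch for an error that leaves the trial short. It does not: 15 is more than enough at d = 1.5, so the mismatch alone is conservative and shows under-reporting. Section 7.0 also says openly that budget and duration mainly set n, calls the study a pilot, and refers to Figure 4 for power at other effect sizes.

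**Conclusion.** The point holds in this form: the printed older-adult muscle results do not support d = 1.5, nor 90% power at the effects observed. The implied paired effects are about 0.74 (Vmax) and 0.27–0.32 (Pmax), and no seventh subject, rounding or between-condition version of d (equal SDs, non-negative correlation) reaches 1.5.

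The practical gap is modest and uncertain for Vmax, where power at n=20 is 0.88 and a favourable seventh subject would remove the shortfall. It is large for Pmax, where power stays below 0.90 at n=15 and n=20 even in the most favourable case. These power figures assume a two-sided paired test at α = 0.05 and trial doses that do no better than the unprinted pilot dose.

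The failure to reproduce n=15 is secondary. The choice of n=20, made mainly on budget and duration, is not undermined. What needs correcting is the stated basis for the power.

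**What to change.** Keep n=20 and restate the sample-size paragraph in Section 7.0:

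- Name the endpoint, contrast, test, sidedness and version of d behind the calculation.
- Show the data that give 1.5, or remove the attribution to the older pilot subjects. If a larger effect is expected at the trial doses, present it as an assumption.
- State the detectable effect at 90% power: a paired d of about 0.90 with 15 completers and 0.76 with 20 for a simple paired test, or about 0.87 and 0.74 if the mixed model's pooled error with 2n−4 df is assumed.
- State that power is lower at the printed pilot effects, especially for Pmax, unless Figure 4 already shows this.
- Reconcile the six subjects in the Preliminary data text with n=7 in Table 1 and Section 7.0.

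The cost is rewording one paragraph, with no change to participants, design or analysis. The stated power will look less favourable.
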